Influence of Vorapaxar on Thrombin Generation and Coagulability

Principal Investigator: [name]

Sub-Investigator(s):

Sponsor: MERCK & Co., Inc.

Site of Investigation:

Inova Heart and Vascular Institute at Inova Fairfax Hospital, VA

Date of Protocol: 08 August 2016

Title: Influence of Vorapaxar on Thrombin Generation and Coagulability**Short Title:** Vorapaxar and Thrombin Generation

Rationale: PAR-1 receptor inhibition is an emerging therapeutic strategy in patients who have suffered ACS. Vorapaxar is a novel antiplatelet agent that selectively inhibits the cellular actions of thrombin through antagonism of PAR-1. Currently, there are no data available regarding the effect of vorapaxar on clot generation kinetics or TIP-FCS when added to standard of care antiplatelet regimens. Potential reduction of TIP-FCS and clot generation kinetics by vorapaxar may assist in our understanding of the mechanism of action and in personalizing therapy in high risk patients to effectively reduce recurrent thrombotic event occurrences.

Objectives: To determine onset-, maintenance-, and offset-effect of vorapaxar on thrombin generation kinetics (clotting time, thrombin generation, platelet-fibrin clot strength, and clot lysis) in antiplatelet naïve patients and patients on mono and dual antiplatelet therapy.

Study Type: Experimental study design

Study Design: This phase IV, prospective cohort (4 groups), non-randomized, open label, pharmacodynamics, and safety investigation.

Study Methodology: This investigation will be conducted in patients 18-75 years of age with multiple coronary artery disease risk factors (antiplatelet naïve patients) and patients with prior MI or PAD on antiplatelet therapy. Pharmacodynamics will be assessed at multiple time points to assess onset-, maintenance-, and offset-effect of vorapaxar on thrombin generation, platelet reactivity, and plasma/platelet endothelial and inflammatory biomarkers. Safety assessment will be assessed throughout the study.

The cohorts include:

Subjects with Multiple Risk Factors:

Group 1: Subjects with multiple risk factors and antiplatelet naïve (n=25).

Group 2: Subjects with multiple risk factors and antiplatelet naïve. 75mg QD clopidogrel QD for ≥ 7 days (n=25).

Subjects with Prior MI or PAD:

Group 3: Subjects with 81mg QD Enteric Coated (EC) Acetylsalicylic Acid (ASA) (n=25).

Group 4: Subjects with 81mg QD EC ASA+75mg QD clopidogrel (n=25).

Statistical Methodology: A very brief description of main elements of the statistical methodology to be used.

1 INTRODUCTION

1.1 Specific Aims

- To determine onset-, maintenance-, and offset-effect of vorapaxar on thrombin generation kinetics (clotting time, thrombin generation, platelet-fibrin clot strength, and clot lysis) in antiplatelet naïve patients and patients on mono and dual antiplatelet therapy.
- To determine onset-, maintenance-, and offset-effect of vorapaxar on platelet reactivity induced by ADP, collagen, arachidonic acid, and SFLLRN.
- To determine the effect of vorapaxar on plasma platelet/endothelial and inflammatory biomarkers in antiplatelet naïve patients and patients on mono and dual antiplatelet therapy.

Hypothesis

- Vorapaxar will reduce TIP-FCS, clot generation kinetics, and plasma biomarkers associated with haemostasis and inflammation in patients on standard of care antiplatelet regimens.
- Vorapaxar effects will be more marked in patients with high TIP-FCS, a risk factor for post-PCI ischemic events.

1.2 Background and Significance

The occurrence of coronary arterial thrombotic events during acute coronary syndromes (ACS) and percutaneous coronary interventions (PCI) are critically dependent on reactive platelets. Antiplatelet therapy plays a central role in preventing stent thrombosis and recurrent myocardial infarction in these high risk patients. Platelet activation involves multiple signaling pathways activated by thrombin, thromboxane A₂, adenosine diphosphate (ADP) and collagen that interact with specific receptors. Simultaneous and optimal blockade of these pathways is essential to ensure effective inhibition of platelet function and attenuation of thrombotic events. However, it remains unclear which pathway is central to the generation of thrombotic events in an individual patient. Emerging data suggests that activation of the protease-activated receptors (PARs) by thrombin and platelet-dependent thrombin generation may be patient specific. Evidence for this concept is present in the significant residual risk (~10%) present in high risk patients treated with potent P2Y₁₂ blockers and ASA.

Translational antiplatelet therapy studies thus far have largely focused on the measurement of platelet aggregation and agglutination to fibrinogen-coated beads in anticoagulated blood. These studies ignore the characteristics of platelet-fibrin clot formation as a potential contributor to the development of adverse events (i.e. no study of platelet-fibrin interactions). In addition to platelet function, thrombin mediated platelet-fibrin clot characteristics may play an important role in the development of ischemic events and stent restenosis. In support of this hypothesis, the POST-STENTING study clearly demonstrated that studying platelet function in isolation may have an important limitation in predicting ischemic events as well as determining effective strategies to reduce recurrent adverse events. In the latter study, we found that high platelet reactivity was a comparatively poor indicator of ischemic events following stenting, relative to measurements of platelet-fibrin clot characteristics.

Adverse events were more or less equally distributed in the middle two quartiles of post-treatment platelet aggregation. Most importantly, thrombin-induced maximum platelet-clot strength (TIP-FCS) measured at discharge was the most powerful predictor of 6 months post-stenting ischemic events with a sensitivity of 74%, specificity of 89%, and odds ratio 22.6 (1st quartile vs. 4th quartile). In the

latter study, 74% of patients with ischemic events had high TIP-FCS (>72 mm, upper quartile value). These results indicate that platelet-fibrin clot strength may play important roles in the development of adverse ischemic events. Those subjects who form the most robust platelet-fibrin clots carry the greatest risk for recurrent thrombotic event occurrence. Of critical importance, these results also indicate that current long term antiplatelet therapies are inadequate to reduce adverse events in selected patients. Novel, longer-term treatment strategies directed at reducing thrombin function in selected patients may have significant impact in reducing adverse events.

Thrombin potently activates platelets through the protease-activated receptor (PAR-1). PAR-1 receptor inhibition is an emerging therapeutic strategy in patients who have suffered ACS. Vorapaxar is a novel antiplatelet agent that selectively inhibits the cellular actions of thrombin through antagonism of PAR-1. In the TRA 2P trial, in patients with a history of heart attack or with peripheral arterial disease (PAD) who had no history of stroke or transient ischemic attack (TIA), vorapaxar added to standard of care was associated with a significant 17 percent relative risk reduction over the three years in the combined events of cardiovascular (CV) death, myocardial infarction (MI), stroke, and urgent coronary revascularization (UCR) [event rate 10.1 percent vs. 11.8 percent for placebo]. For the key secondary composite efficacy endpoint of CV death, MI, and stroke alone, vorapaxar produced a significant 20 percent relative risk reduction in these patients [7.9 percent vs. 9.5 percent for placebo]. Based on these results, the U.S. Food and Drug Administration recently approved Zontivity (vorapaxar) to reduce the risk of heart attack, stroke, and cardiovascular death for secondary prevention in patients with a history of MI and peripheral vascular disease.

Currently, there are no data available regarding the effect of vorapaxar on clot generation kinetics or TIP-FCS when added to standard of care antiplatelet regimens. Potential reduction of TIP-FCS and clot generation kinetics by vorapaxar may assist in our understanding of the mechanism of action and in personalizing therapy in high risk patients to effectively reduce recurrent thrombotic event occurrences.

[figure not shown]
2 STUDY DESIGN AND SUBJECT SELECTION

2.1 Study Type

This phase IV, open label, pharmacodynamic investigation will be conducted in patients 18-75 years of age with multiple coronary artery disease risk factors (antiplatelet naïve patients) and patients with prior MI or PAD on antiplatelet therapy (Figure 1). All Subjects will be enrolled at Inova Fairfax Medical Center. Enrollment is expected to be completed within 6-8 months after first individual is enrolled. Informed consent will be obtained from subjects meeting the inclusion criteria before the initiation of any study-specific procedures. Pharmacodynamics will be assessed at multiple time points to assess onset-, maintenance-, and offset-effect of vorapaxar on thrombin generation, platelet reactivity, and plasma/platelet endothelial and inflammatory biomarkers. Safety assessment will be assessed throughout the study.

Figure 1

Influence of Voropaxar on Thrombin Generation and Coagulability

PD Measurements

- Thrombin generation kinetics by TEG-6S and Thrombovision
- 5uM ADP-, 15 uM SFLLRN (PAR-1) and 4ug/ml collagen-induced aggregation by LTA and TEG-6S
- Plasma platelet/endothelial and inflammatory biomarkers

Safety Assessments

- Safety labs and physical assessment at screening, 24 hrs, 3-4 weeks, and at end of study
- SAE and AE collection

2.2 Number of Subjects

Multiple cohorts of subjects may be utilized in order to achieve the target enrollment number of 100 subjects (25 qualified subjects in each study group) with valuable data.

2.3 Study Population

2.3.1 Population Characteristics

2.3.1.1 Demographics

Demographic data will be collected at the screening visit. These data will include:

- Gender
- Date of birth
- Race/ ethnicity

2.3.1.2 Medical history

Medical history which includes previous diagnoses, diseases, surgeries, smoking history and concomitant medications will be collected.

2.3.2 Gender of Subjects

The study's intended population is inclusive of both sexes/genders (males and females), and all racial and ethnic groups and subgroups. Female subjects are eligible for participation in the study only if they are of non-childbearing potential (i.e., physiologically incapable of becoming pregnant).

2.3.3 Age of Subjects

Subject enrollment will be comprised of men and women between 18 and 75 years of age with history of myocardial infarction and/or peripheral artery disease, or who have ≥ 2 risks factors of developing cardiovascular disease (type 2 diabetes, obesity, current smoking, hypertension, hypercholesterolemia, history of a thrombotic event while on ASA therapy).

2.3.4 Vulnerable Populations

Vulnerable population will not be included as it is not appropriate for the scientific goals of the research proposed.

2.4 Recruitment

Recruitment will occur at the Inova Heart and Vascular Institute. The length of the recruitment period is 8.5 months. Multiple strategies will be employed to identify potentially eligible subjects for this study. These will include (but are not restricted to) database screening, chart screening, and patient screening at physician offices and at internal medicine, cardiology, and vascular disease/imaging clinics.

If the study conduct (e.g. recruitment rate; drop-out rate; data quality; protocol compliance) does not suggest a proper completion of the trial within the reasonable time frame as agreed upon, the recruitment period may be extended to reach the desired sample size.

2.5 Inclusion Criteria

The study will include subjects who have multiple risk factors of developing atherosclerosis or evidence or a history of atherosclerosis involving the coronary or peripheral vascular systems. Subjects may be enrolled if they appropriately fulfill all inclusion criteria and none of the exclusion criteria.

Inclusion Criteria: Subjects must meet ALL the criteria listed below for entry:

1. Subject may be of either sex and of any race, and must be between 18 and 75 years of age.
2. Subject must have multiple risk factors of developing atherosclerosis, or evidence of a history of atherosclerosis involving the coronary or peripheral arterial systems as follows:
 - a. Subject must present with multiple risk factors for CAD or PAD such as high blood pressure, high cholesterol, diabetes, obesity, current smokers, 55 years or older, or
 - b. CAD as indicated by a history of presumed spontaneous MI (hospitalized with final diagnosis of MI, excluding periprocedural or definite secondary MI due to profound anemia or hypertensive emergency or troponin increase in sepsis) at least 1 month prior to enrollment, or
 - c. PAD as indicated by a history of intermittent claudication and
 - i. a resting ankle/brachial index (ABI) of <0.85 , or

- ii. significant peripheral artery stenosis (>50%) documented by angiography or non-invasive testing by duplex ultrasound, or
 - iii. previous limb or foot amputation for arterial vascular disease (excludes trauma), or
 - iv. previous aorto-femoral bypass surgery, limb bypass surgery or percutaneous transluminal angioplasty of the iliac or infrainguinal arteries.
3. Subject must be willing and able to give appropriate informed consent.
 4. The subject is able to read and has signed and dated the informed consent document including authorization permitting release of personal health information approved by the investigator's Institutional Review Board (IRB).

2.6 Exclusion Criteria

Exclusion Criteria: Subjects will be excluded from entry if ANY of the criteria listed below are met:

1. Clinically unstable at the time of enrollment.
2. Any planned coronary revascularization or peripheral intervention.
3. Concurrent or anticipated treatment with warfarin (or derivatives, e.g., phenprocoumon), oral factor Xa inhibitor, or oral direct thrombin inhibitor after enrollment.
4. Concurrent or anticipated treatment with a potent inducer (e.g., rifampin) or potent inhibitor (e.g., ketoconazole, erythromycin) of CYP3A4 isoenzymes (see Appendix B) (but see note in text for exceptions).
5. History of a bleeding, or evidence of active abnormal bleeding.
6. History at any time of intracranial hemorrhage, intracranial or spinal cord surgery, or a central nervous system tumor or aneurysm.
7. Documented sustained severe hypertension (systolic blood pressure >200 mmHg or diastolic blood pressure >110 mmHg) at enrollment or within the previous 10 days.
8. Severe valvular heart disease, as defined by the American College of Cardiology /American Heart Association.
9. History within 30 days before enrollment of invasive surgeries (other than mentioned above), or is anticipating one during the course of their study participation, or is planning to have one within 1 month post dosing with the study drug.
10. History within 30 days before enrollment of TIA and ischemic (presumed thrombotic) stroke/CVA.
11. Known platelet count <100,000/mm³ within 30 days before enrollment.
12. Known active hepatobiliary disease, or known unexplained persistent increase in serum alanine aminotransferase (ALT) or aspartate aminotransferase (AST) activity to two times or more the upper limit of the reference range (upper limit of "normal" [$\uparrow 2 \times \text{ULN}$]).
13. Any serious illness or any condition that the investigator feels would (a) pose a significant hazard to the subject if investigational therapy were initiated, or (b) would limit the prognosis of the subject, regardless of investigational therapy.
14. Any serious medical comorbidity (e.g., active malignancy) such that the subject's life expectancy is <24 months.
15. Known current substance abuse at the time of enrollment.
16. Current participation in any other study of investigational therapy or participation in such a study within the last 30 days.
17. Known hypersensitivity to any component of the current investigational product.
18. Female subject of child-bearing potential.

19. Subject is a woman who is breast-feeding.
20. Subject is part of the staff personnel directly involved with this study or is a family member of the investigational staff.

3 Treatments

3.1 Treatments to Be Administered

The study drugs to be administered in this trial include the: PAR1 antagonist, vorapaxar; enteric coated (EC) Acetylsalicylic Acid (ASA); and P2y12 inhibitor, clopidogrel.

3.1.1 Run-in

Eligible subjects (excluding subjects in group 1) who have signed informed consent will complete the run-in period. Subjects will be instructed to continue on their prescribed antiplatelet regimen, EC ASA and/or clopidogrel; however, the medications will be provided to the subjects by the study site for compliance accounting purposes. Study diaries will be provided for the run-in period only (7 -10 days) and pill reconciliation will be performed for all visits. The subjects will postpone taking their antiplatelet regimen in order to take the dose during this visit from the medication provided by the study site. Subjects will be assigned into the following groups:

- Subjects in group 2 will receive clopidogrel 75mg orally daily provided by the study site. Subjects in group 3 will receive EC ASA 81 mg orally daily provided by the study site.
- Subjects in group 4 will receive clopidogrel 75mg in addition to EC ASA 81mg orally daily provided by the study site.

Subjects will be grouped according to their current antiplatelet regimen. Subjects with cardiovascular risk factors not on antiplatelet therapy will be included in either Group 1 or 2. Patients on ASA alone will be included in Group 3 and patients on dual antiplatelet therapy will be in Group 4. All doses will be in tablet form for oral administration.

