4.8 Study Treatment/Intervention-

This phase IV, open label, pharmacodynamic investigation will be conducted in patients between 18-75 years of age with multiple coronary artery disease risk factors (antiplatelet naïve patients) and patients with prior MI or PAD on antiplatelet therapy (Figure 1). Informed consent will be obtained from subjects meeting the inclusion criteria before the initiation of any study-specific procedures. Subjects will be grouped according to their current antiplatelet regimen. Subjects with cardiovascular risk factors not on antiplatelet therapy will be included in either Group 1 or 2. Patients on ASA alone will be included in Group 3 and patients on dual antiplatelet therapy will be in Group 4.

- Group 1 (control group): vorapaxar 2.08mg orally once daily
- Group 2: clopidogrel 75mg orally once daily + vorapaxar 2.08mg orally once daily
- Group 3: EC aspirin 81mg orally once daily + vorapaxar 2.08mg orally once daily
- Group 4: EC aspirin 81mg orally once daily + clopidogrel 75mg orally once daily + vorapaxar 2.08mg orally once daily

The study comprises 6 periods: screening, run-in (for subjects in groups 2, 3, and 4), onset and maintenance, offset, and end of study (Figure 1). The trial will require clinic visits at screening, vorapaxar dosing day, 24 hours post initial vorapaxar dosing, 3-4 weeks post-dosing, 2 weeks post vorapaxar discontinuation, and 4 weeks post vorapaxar discontinuation. Patient instructions for the run-in phase will be given during the screening visit. One day prior to the run-in, the study coordinator will call the subject to remind subjects of run-in instructions.

Pharmacodynamics will be assessed at multiple time points to assess onset-, maintenance-, and offset-effect of vorapaxar on thrombin generation, platelet reactivity, and plasma/platelet endothelial and inflammatory biomarkers. Safety assessment will be assessed throughout the study. Approximately 25-30ml of blood will be drawn at each visit. Phlebotomy sites will be carefully chosen to minimize risk. See schedule of procedures in section 7 for detailed schedule of study events.

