5 STATISTICAL CONSIDERATIONS/DATA ANALYSIS

5.1 Sample Size

This is an exploratory study; we assume that a sample size of 25 qualified subjects (see study schematic) in each group is sufficient to assess the difference in platelet inhibitory effect of vorapaxar 2.08 mg, administered alone or in addition to an antiplatelet agent (clopidogrel 75mg), and/or acetylsalicylic acid 81mg.

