5.2 Primary and Secondary Analysis

5.2.1 Primary Analysis

The primary endpoint measures are a change in platelet-fibrin clot generation kinetics by thrombelastography (R, TIP-FCS, TG) and thrombin generation kinetics (Lag time, peak thrombin production, time to peak thrombin generation, and endogenous thrombin potential) as measured by calibrated automated thrombogram at maintenance therapy (3-4 weeks vorapaxar treatment) compared to pre-dose within and between each treatment group.

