5.2.2 Secondary Analysis

Secondary Analysis endpoint measures are a change in:

- Platelet-fibrin clot generation kinetics by thrombelastography (R, TIP-FCS, TG) at onset and offset vorapaxar treatment compared to pre-dose within and between each treatment group.
- Thrombin generation kinetics (Lag time, peak thrombin production, time to peak thrombin generation, and endogenous thrombin potential) as measured by calibrated automated thrombogram during onset and offset of vorapaxar treatment compared to pre-dose within and between each treatment group.
- 5 μ M ADP-, 15 μ M SFLLRN (TRAP)-and 4 μ g/ml collagen- induced maximal and final aggregation by light transmittance aggregation during onset, maintenance, and offset of vorapaxar treatment compared to pre-dose within and between each treatment group. ADP-and

AA-induced aggregation by TEG-6S Platelet Mapping assay during onset, maintenance, and offset of vorapaxar treatment compared to pre-dose within and between each treatment group.

- Platelet/endothelial and inflammatory biomarkers during onset, maintenance, and offset of vorapaxar treatment compared to pre-dose within and between each treatment group. Reactive hyperemia index (RHI) as assessed using the ENDOPAT system between pre-dose and maintenance therapy within and between the treatment groups.

6 Statistical calculations

Statistical calculations will be carried out using SAS® for Windows, version 9.3 or later (Cary, NC). Within group analyses of change scores (pre and post vorapaxar) will be performed using a paired t-test, or the Wilcoxon signed ranks test if the change scores are sufficiently non-normal. The Shapiro-Wilk test will be used to determine if the change scores are non-normal. A calculated P-value < 0.05 will be considered a significant difference between treatments. A secondary ANCOVA analysis will be performed in each group to examine the factors that explain potential variations in change scores, and model variables will include the baseline test value, age, sex, race, weight, diabetes, antiplatelet response to EC ASA and clopidogrel, smoking, etc.

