The study coordinator will call the eligible subjects the day before to review protocol instructions and study related activities for Visit 2 and answer any potential questions. Remind the subjects to hold their clopidogrel and/or EC ASA (study medications) and all other medications taken by the subjects regularly. Subjects will be instructed to bring all home medications with them for the appointment to take after the bloodwork and testing. Ask subjects to avoid any high fat foods the morning of the visit. For the Endo-PAT2000 test, the subject needs to abstain from smoking and caffeine 2 hours prior to testing. Subjects also need to hold any vasoactive medications 24 hours prior to the test.

The dosing visit will occur within 3 to 28 days of screening for subjects in group 1. Visit 2 for groups 2, 3, and 4 will occur within 7 + 3 days from the run-in period.

During this visit, the following procedures will be performed:

- Vital signs (blood pressure, heart rate) will be obtained after the subject has been in a sitting position for at least 5 minutes.
- Collection of Study Drug Diary for subjects in groups 2, 3, and 4.
- Study drug accountability will be performed (groups 2, 3, and 4).
- Administer Endo-PAT2000 test.
- Blood and urine samples will be obtained for baseline PD measurements through direct venipuncture. The actual date and clock time of blood/urine sampling will be recorded in the CRF.
- Provide a small snack after blood and urine specimen collection
- If applicable, after lab work collection and endo-PAT2000 test, remind subject to take approved home medications as according to subject's regular schedule. Subjects will receive first dose of vorapaxar 2.08mg orally. After administering first dose of vorapaxar, administer daily dose of study treatment (clopidogrel and/or EC ASA) to subjects as according to assigned group (to prevent a missing dose).
- Subject will return to clinic in 2 hours (+ 60 mins) post vorapaxar dosing time for PD blood draw.
- Collection of adverse events.
- Collection of concomitant medications.
- Dispense study drugs
 - Group 1: A bottle of 37 tablets of vorapaxar 2.08mg
 - Group 2: A bottle of 37 tablets of vorapaxar 2.08mg and 37 tablets of clopidogrel 75mg
 - Group 3: A bottle of 37 tablets of vorapaxar 2.08mg and 37 tablets of EC ASA 81mg.
 - Group 4: A bottle of 37 tablets of vorapaxar 2.08mg, 37 tablets EC ASA 81mg, and 37 tablets of clopidogrel 75mg.
- Provide patient education for vorapaxar

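### If Group 2 is antiplatelet-naive at entry, no readable rule decides who joins Group 1 or Group 2, leaving that between-group contrast open to selection

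*Combined protocol and SAP*

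**What the plan says.** **Who enters Groups 1 and 2.** The synopsis defines Group 1 as antiplatelet-naive people with multiple risk factors (n=25). It gives the second group the same entry description, "Group 2: Subjects with multiple risk factors and antiplatelet naïve", and adds clopidogrel for at least 7 days (n=25). Section 3.1.1 groups subjects by their current regimen and then says "Subjects with cardiovascular risk factors not on antiplatelet therapy will be included in either Group 1 or 2". Section 4.8 repeats this and adds no criterion. The synopsis calls the study non-randomised and open label.

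**What the contrast is for.** Section 4.8 lists "Group 1 (control group): vorapaxar 2.08mg orally once daily". Section 5.2.1 defines the primary endpoint as change "at maintenance therapy (3-4 weeks vorapaxar treatment) compared to pre-dose within and between each treatment group". Section 5.1 calls the study exploratory and justifies 25 per group by the difference in effect between vorapaxar alone and vorapaxar on top of clopidogrel and/or aspirin.

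**What is analysed.** Section 6 states: "Within group analyses of change scores (pre and post vorapaxar) will be performed using a paired t-test", with a signed-rank alternative. It then adds: "A secondary ANCOVA analysis will be performed in each group to examine the factors that explain potential variations in change scores". No between-group test or model is named.

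**The concern.** Groups 3 and 4 are fixed by what patients already take. Groups 1 and 2, as the synopsis and sections 3.1.1 and 4.8 describe them, take nothing at entry, so the study itself decides who gets clopidogrel. Staff preference, subject preference or filling one group before the other would all comply with the text. Any of these could relate to age, diabetes, smoking or something unrecorded that also affects the response to vorapaxar.

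Groups 3 and 4 also differ from Group 1 by prior MI or PAD. Group 1 versus Group 2 is therefore the only contrast with the control group that is not confounded by disease category at entry. It is also the one whose comparability the protocol could secure by design, and allocation cannot be repaired after enrolment.

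**Working it through.** No figure in the plan can be reproduced here: section 5.1 gives no effect size, SD or power for the 25 per group. The check is a reading of the text, followed by an illustration of scale.

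**1. Is there an assignment rule?** Sections 3.1.1 and 4.8 offer one principle, current regimen. It places aspirin users in Group 3 and dual-therapy users in Group 4. For people on no antiplatelet it returns the same answer for Groups 1 and 2. The readable text gives no list, alternation, enrolment order, matching or clinical criterion.

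**2. Is Group 2 certainly naive at entry?** The text conflicts.

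| Naive at entry | Suggests otherwise |
|---|---|
| Synopsis: Group 2 described as naive | 3.1.2: attaches the naive label to Group 1 only |
| 3.1.1 and 4.8: subjects on no antiplatelet go to Group 1 or 2 | 3.1.1 and 9.2.2: run-in subjects carry on with a prescribed regimen; 9.2.2 has them hold home clopidogrel and/or aspirin |
| | 9.2.1: home aspirin and clopidogrel continue until the next visit |
| | 9.2.7: return, if applicable, to the original aspirin and/or clopidogrel dose |

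Much of the right-hand column is shared wording for Groups 2 to 4, so it does not settle the matter. If Group 2 may enter on clopidogrel, current regimen does separate those subjects from Group 1.

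**3. Does any planned analysis deal with selection?** The paired test uses one group at a time. The ANCOVA lists useful covariates (baseline value, age, sex, race, weight, diabetes, smoking), but it is fitted in each group separately. It has no group term and cannot adjust a difference between groups.

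**4. Are the two groups filtered alike?** Under 3.1.2, Group 2 must complete a run-in with no more than 2 missed doses; Group 1 has no run-in. Section 4.7 limits CYP2C19 testing, with exclusion of poor metabolisers, to candidates for Groups 2 and 4, whereas Table 1 and 9.2.1 schedule the swab for everyone.

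**5. Would adjusting for the pre-dose value help?** At Visit 2 (section 9.2.3), "Blood and urine samples will be obtained for baseline PD measurements through direct venipuncture". For Group 2 this follows the clopidogrel run-in, so the value may already reflect the background drug. It is not a measure of comparability at entry.

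**6. Scale, by assumption only.** Inputs: 25 per group (5.1); a two-sided 5% two-sample t test, assumed because the plan names none; no true group difference; a selection shift b in SD of change, assumed.

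- SE = sqrt(2/25) = 0.283 SD.
- 95% CI half-width = t(0.975, 48 df) × SE = 0.569 SD.
- Relative to the half-width: 0.15/0.569 = 26%; 0.40/0.569 = 70%.
- Rejection rate from the noncentral t distribution, 48 df, noncentrality b/SE:

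| Assumed shift b (SD) | False-positive rate |
|---|---|
| 0.15 | 8.1% |
| 0.28 | 16.3% |
| 0.40 | 28.3% |

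A shift of 0.15 SD would arise, for example, from a factor whose prevalence differs by 30 percentage points between groups and which moves the change by 0.5 SD (0.30 × 0.5 = 0.15). At 0.1 SD the rate is 6.4% (normal approximation), close to nominal.

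**The case against.** The strongest reply is that the design is openly non-randomised and exploratory, and neither stated hypothesis is specific to this pair. Group 1 versus Group 2 is one of six pairwise contrasts (4 × 3/2), and asking for randomisation changes a declared design. This limits the weight of the point. It does not remove it: declaring a study non-randomised does not say who goes where, and a reader needs that rule to judge a contrast that forms part of the primary endpoint.

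The second reply is that the premise is uncertain. Group 2 may include people already on clopidogrel, and a rule might sit in Figure 1 or the schematic. Both stand, so the point is conditional. The readable text cites Figure 1 for the overall design and study periods, not for assignment.

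The third reply is that every shift in the illustration is invented. That also stands. A modest imbalance would leave the error rate near 5%, and the upper end has no basis in the documents.

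A reader might infer that selection did bias the comparison, or that the whole primary analysis is compromised. The documents support neither. They show an opening for selection, not selection itself, and each group's pre/post change does not depend on how naive subjects were split. A reader might also infer that the plan adjusts the contrast wrongly for a post-clopidogrel baseline. It does not: its ANCOVA makes no between-group adjustment at all.

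**Conclusion.** The point holds in conditional form. On the readable text, if Group 2 is naive at entry, nothing determines who joins Group 1 and who joins Group 2, and section 6 contains no analysis that could address the consequence. The effect is confined to the Group 1 versus Group 2 difference in change.

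The size and direction of any bias cannot be estimated from the documents. The 8% to 28% range is a sensitivity illustration resting on assumed shifts of 0.15 to 0.40 SD and an assumed t test. It should be corrected before enrolment, though it does not threaten the study as a whole. Confidence is medium, because Group 2's entry status is contradictory and the figures are not shown.

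**What to change.** 1. **Reconcile the text.** State whether Group 2 is naive at entry, and align 3.1.1, 3.1.2, 9.2.1, 9.2.2 and 9.2.7 with the synopsis and 4.8. Reconcile 4.7 with Table 1 and 9.2.1 on who has the CYP2C19 swab.
2. **If Group 2 is naive at entry,** allocate eligible naive subjects 1:1 to Group 1 or 2 from a concealed list after screening, with the same eligibility filters applied before allocation. Amend the non-randomised label for this pair only.
3. **Name the comparison in section 6:** Group 1 versus Group 2 difference in change from pre-dose to maintenance, with a 95% CI. If randomised, the unadjusted difference leads. If not, write down the actual rule, label the contrast non-randomised, and let a model with a group term and variables already collected at screening (age, sex, diabetes, smoking) lead, stating that unmeasured differences remain. Do not make the pre-dose value the lead covariate.
4. **Report run-in losses by group.**

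**Cost.** Randomising needs a protocol amendment and an allocation list, and gives up choice of group; it adds no arm, dose or visit. If Table 1 governs, there are no extra swabs. If 4.7 governs, at least one more is needed per Group 1 subject (25 or more), and poor metabolisers are also lost from Group 1. Keeping non-random assignment costs one sentence stating the rule, a label and one named model.
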